### Post-Surgical Assessment

Patients will be assessed for post-surgical complications (readmission, wound healing, infection) at 1 month +/- 2 weeks post-surgery. Complications will be categorized as related, probably related, possibility related, unlikely related, or unrelated to cetuximab.

Post-surgical adjuvant therapy will be delivered based on standard of care therapy as per recommendations of the University of Wisconsin Multidisciplinary Head and Neck Oncology Tumor Board. Receiving the two doses of cetuximab in the pre-operative setting will not be grounds for exclusion of cetuximab use at a later point. Such usages would include concurrent chemoradiotherapy, palliative combination chemotherapy and/or palliative monotherapy with cetuximab.

Distant metastatic disease and/or unresectable recurrent locoregional disease will be managed as per the institutional standard of care.

Expected duration of subject participation is approximately 13 to 16 months. The time to complete study enrollment is estimated to be 18 months. The time to complete the study analysis is estimated to be 30 months (from time of first patient enrolled to the time of last patient completed treatment).

#### **4.1 Substudies (if applicable)**

Not applicable.

### **5 STUDY ENROLLMENT AND WITHDRAWAL**

This study is anticipated to enroll a target sample size of 36 subjects. We estimate approximately 100 subjects will be screened to reach the target enrollment.

## 5.1 Subject Inclusion Criteria

Adult men and women and members of all races and ethnic groups are eligible for this trial. Persons with impaired decision-making capacities will not be eligible for enrollment in this study. Eligibility criteria will be assessed via clinical labs, review of medical records as well as self-reporting. Subjects will be recruited from the University of Wisconsin Hospital and Clinics.

Step 1 registration will occur when subject has signed consent and consent has been registered (added) to ONCORE.:

- Age  $\geq$  18 years
- Informed consent: patients must be informed of the investigational nature of the study and must be able to sign a written informed consent.
- Inclusion criteria for research biopsy (screen)
  - Patients must have suspected or known clinical presentation of head and neck squamous cell carcinoma or a recurrence of head and neck squamous cell carcinoma after initial therapy. For newly suspected head and neck cancer, the procedure will obtain tissue for both standard of care biopsy and additional tissue for research.
  - Participants must have sufficient tumor volume (approximately 10 cc) to accommodate at minimum 2-3 core samples for the research biopsy. This will be approximated based on clinical evidence, such as physician visualization or palpitation.
  - Patients are required to consent to the TSB Biobank protocol (2016-0934) as part of this study.
  - Surgical management must be the chosen modality for management of the head and neck squamous cell cancer.
    - Other therapeutic modalities may follow, but surgery must be the choice for first therapy rendered.

For Step 2 enrollment on this study an individual must meet all criteria for Step 1 and the following criteria:

- Inclusion criteria for cetuximab treatment:
  - Patients must have a biopsy proven, squamous cell carcinoma of the head and neck, excluding advanced cutaneous head and neck squamous cell carcinoma.
  - ECOG performance status  $\leq$  1
  - Women of childbearing potential (WOCP) must not be pregnant (confirmed by a negative urine/serum pregnancy test within 7 days of cetuximab treatment). In addition, a medically acceptable method of birth control must be used such as an oral, implantable, injectable, or transdermal hormonal contraceptive, an intrauterine device (IUD), use of a double barrier method (condoms, sponge, diaphragm, or vaginal ring

with spermicidal jellies or cream), or total abstinence during the study participation and for 6 months after last dose of study drug. Women who are postmenopausal for at least 1 year or surgically sterile (bilateral tubal ligation, bilateral oophorectomy, or hysterectomy) are not considered to be WOCP.

- Men who are not surgically or medically sterile must agree to use an acceptable method of contraception. Male patients with female sexual partners who are pregnant, possibly pregnant, or who could become pregnant must agree to use condoms during the study and for 6 months post study drug. Total abstinence for the same study period is an acceptable alternative.
- Patients with other concomitant malignancies are allowed to participate on the clinical trial as long as the surgical resection of the head and neck squamous cell carcinoma is clinically indicated.
- Patients with metastatic disease are allowed to participate on the clinical trial as long as the surgical resection of the head and neck squamous cell carcinoma is clinically indicated.

•

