## **4 STUDY DESIGN**

This clinical trial is a single-site, single arm, open label, window of opportunity study for patients with squamous cell carcinoma of the head and neck. Subjects (targeted N=36) are patients who have biopsy-proven, squamous cell carcinoma of the head and neck, excluding advanced cutaneous head and neck squamous cell carcinoma, who are anticipated to undergo surgical resection of the tumor, and who are candidates for cetuximab pre-operative therapy. Patients with newly diagnosed cancer or those who present with recurrent disease are eligible for this trial. All patients will undergo a research biopsy (in clinic or at the time of panendoscopy—not standard of care) and a staging workup with cross-sectional imaging of the neck (standard of care).

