  - history of arterial or venous thrombosis/thromboembolic event, including pulmonary embolism within 6 months of study enrollment
  - any condition requiring the use of immunosuppression, excluding rheumatologic conditions treated with stable doses of corticosteroids
  - Use of herbal supplements (St. John's Wort, gingko biloba, etc.) within one week of cetuximab treatment

For patients who do not meet eligibility criteria for Step 2 of the study, the tissue from the research biopsy will be released to the TSB Biobank or back to surgical pathology if needed for a clinical diagnosis.

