## 7.1 Screening / Baseline Visit (Day -21 to 1)

### Study Visit 1 and 2

- Informed consent/HIPAA authorization obtained prior to any research procedures. Subjects will also be required to sign biobanking consent for banking of residual study samples. (research-related)
- Demographics (recorded for the study from medical records maintained as part of standard clinical care)
- Medical history including prior therapies and pathology (recorded for the study from medical records maintained as part of standard clinical care)
- Concomitant medications (recorded for the study from medical records maintained as part of standard clinical care)
- Physical exam, height (screening only), weight (recorded for the study from medical records maintained as part of standard clinical care)
- Vital signs (blood pressure, heart rate, temperature) (recorded for the study from medical records maintained as part of standard clinical care)
- ECOG performance status (recorded for the study from medical records maintained as part of standard clinical care)
- CBC with differential (recorded for the study from medical records maintained as part of standard clinical care)
- Blood chemistries (sodium, potassium, chloride, bicarbonate, BUN creatinine, glucose, AST, ALT, Alk Phos, T. bili, calcium, magnesium,
- T. protein and albumin (recorded for the study from medical records maintained as part of standard clinical care)
- Within 7 days prior to initiation of cetuximab: Urine pregnancy test for women of childbearing potential (WOCP). If the urine test is positive or cannot be confirmed as negative, a serum pregnancy test will be required. (standard clinical care for CTX administration)
- Adverse event evaluation (standard clinical care for CTX administration)
- Research biopsy for biological correlative studies
- Research blood draw for analysis of circulating tumor cells/biomarkers
- Measurement of tumor size via clinical assessment (research-related)

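### The ECOG limit and the contraception agreement are first required at Step 2, after the non-standard research biopsy, although both can be checked before it

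*Combined protocol and SAP*

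**What the plan says.** Section 5.1 sets two gates. The first is headed "Inclusion criteria for research biopsy (screen". With age and consent, it asks for suspected, known or recurrent head and neck squamous cell carcinoma, enough tumor volume, biobank consent, and surgery as the first therapy. The second gate is headed "Inclusion criteria for cetuximab treatment" and is cumulative: "For Step 2 enrollment on this study an individual must meet all criteria for Step 1 and the following criteria". It adds biopsy-proven histology, ECOG 1 or lower, pregnancy status and contraception.

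Section 4 describes the procedure behind the first gate: "All patients will undergo a research biopsy (in clinic or at the time of panendoscopy—not standard of care". Section 7.1 puts the biopsy, the research blood draw and this item in one block for Study Visits 1 and 2: "ECOG performance status (recorded for the study from medical records maintained as part of standard clinical care". Section 5.2 deals with tissue already taken when "patients who do not meet eligibility criteria for Step 2 of the study, the tissue from the research biopsy will be released" to the biobank or back to surgical pathology. Section 5 gives the scale: "We estimate approximately 100 subjects will be screened to reach the target enrollment", the target being 36.

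**The concern.** A two-step registration makes sense for a fact that the biopsy itself supplies, namely histology. ECOG status and willingness to use contraception are not such facts. Placing them at the second gate lets a patient accept a procedure done for research and then be turned away on something that could have been known beforehand.

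At stake are the risks that Section 2.2.1 lists for the biopsy (bleeding, infection, brief pain) and for the blood draw, carried by someone whose sample cannot serve the question of AXL and response. The primary analysis, the power and the validity of the AXL comparison are not affected.

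**Working it through.** No figure in the plan needs reproducing here. The check sets the eligibility lists side by side and then bounds the number of patients.

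**Step 1. Where each criterion sits**

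| Criterion | Step 1 (5.1) | Step 2 (5.1) | Exclusion (5.2) | Knowable before the biopsy? |
|---|---|---|---|---|
| ECOG 1 or lower | no | yes | no | yes, recorded at screening (7.1) |
| Contraception agreement | no | yes | in part: plans to conceive or father a child | yes, by asking |
| Not pregnant | no | yes, test within 7 days of cetuximab | yes | in part; the test is tied to dosing |
| Proven squamous histology | no, suspicion is enough | yes | certain tumor types | often not in new cases |
| Cardiac, vascular, allergy and recent-therapy history | no | no | yes, for the whole study | yes |

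Only the first two rows combine absence from Step 1, no full cover in Section 5.2, and a fact available beforehand. ECOG is the clearer of the two, because Section 5.2 does not mention it.

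**Step 2. Follow one patient through the text.** Take a consenting adult with recurrent disease, adequate tumor volume, surgery chosen and ECOG 2. Every Step 1 item is met. The biopsy and the blood draw follow, and Step 2 then fails. In Appendix A, ECOG is scheduled at Visits 1 and 2 and not again until Visit 5, after both doses. The only scheduled record before dosing is therefore in the same block as the biopsy. No sentence says that it must be read first. Section 14.1 requires a signed eligibility checklist before enrollment, but Section 5.1 speaks of registration at Step 1 and enrollment at Step 2, so the checklist does not clearly come before the biopsy.

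**Step 3. What the sample can be used for.** Section 12.2 requires both complete doses and resection for efficacy, molecular or correlative studies and xenograft creation. A patient stopped at Step 2 has neither dose. The same section counts anyone biopsied in the safety evaluation.

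**Step 4. How many.** Not enrolled = screened − target = 100 − 36 = 64. The number affected is 64 × (share biopsied before stopping) × (share of those stopped by ECOG or contraception alone). The documents give neither share. With each between 0 and 1, the range is 0 to 64.

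**The case against.** The strongest reply is that other filters already work ahead of the biopsy. The protocol summary and Section 4 describe participants as candidates for cetuximab, and Section 5.3 has staff review schedules and records for gross eligibility before the physician raises the study. Section 5.2 excludes people with uncontrolled conditions that pose unacceptable risk, and those expecting to conceive or father a child from the screening visit on. For newly suspected cancer, Section 5.1 takes both tissues in one procedure. These points stand as mitigation: they make biopsy of plainly unsuitable patients less likely and lighten the burden. None of them states an ECOG limit at Step 1.

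A reader might infer four stronger things that the documents do not support.

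- *That the medical-history exclusions are also missing before the biopsy.* Section 5.2 opens by excluding people from participation in the study as a whole, and a research biopsy under this consent is participation. What remains is an unclear reference date: several windows run from study enrollment, which is not defined against the two steps.
- *That the rule for tissue from Step 2 failures shows that avoidable failures are planned.* Failed histology explains it. Sections 4 and 8.2.3 describe release of tissue when the diagnosis is not confirmed.
- *That such a patient can never be treated or inform any endpoint.* ECOG may be reassessed before dosing, and Section 12.2 places biopsied patients in the safety evaluation. Patients who fail on histology would enter that evaluation even after the fix, so the safety and halting-rule denominators are a separate matter.
- *That a definite number of biopsies is avoidable.* The plan gives no failure rate by criterion. The 100 screened may include people who stop at record review or fail Step 1 itself.

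**Conclusion.** The point holds in a limited form. Section 5.1 leaves ECOG 1 or lower and the contraception agreement to Step 2, so someone not eligible for protocol cetuximab at that time can have the non-standard research biopsy and blood draw without being able to contribute to the efficacy or correlative endpoints. ECOG carries most of the weight; contraception is partly covered by Section 5.2.

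The size is unknown, between 0 and 64 of about 100 screened. The upper end assumes that everyone not enrolled was biopsied and failed on these two items alone, which nothing in the documents suggests. Where the cancer is newly suspected, the added burden is extra tissue. For recurrent or already proven disease the biopsy may be a separate procedure, but the documents do not say how often. The case for change rests on the low cost of re-ordering, not on a count.

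**What to change.** In Section 5.1, require the existing ECOG criterion and the existing contraception agreement, both unchanged, to be confirmed at Step 1, before the research biopsy and the research blood draw. In Section 5.2, state that the exclusions not depending on histology are checked at the same point, and say which event counts as study enrollment for the time windows. Keep at Step 2 the biopsy-proven histology, the 7-day pregnancy test and a re-check that nothing has changed. Align the eligibility checklist in Section 14.1 with this order.

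The cost is an amendment to Sections 5.1 and 5.2 and to the checklist. No threshold, visit, data item, staff or sample size changes. The downside is fewer Step 2 failure samples for the biobank and a slightly longer check before the biopsy.

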## 5.2 Subject Exclusion Criteria

An individual who meets any of the following criteria will be excluded from participation in this study:

- Diagnosis of nasopharyngeal carcinoma, advanced cutaneous squamous cell carcinoma of the head & neck, and salivary gland tumors
- Other concurrent severe and/or uncontrolled concomitant medical conditions (e.g. active or uncontrolled infection, uncontrolled diabetes) that could cause unacceptable safety risks or compromise compliance with the protocol
- Prior chemotherapy, radiotherapy, or major surgery within 8 weeks of study enrollment or those who have not recovered (to grade ≤ 1 or baseline) from clinically significant adverse events due to agents administered more than 8 weeks earlier (alopecia and fatigue excluded). Clinical significance to be determined by the study investigator
- Prior cetuximab therapy is allowed so long as administered  8 weeks ago.
- History of allergic reactions attributed to compounds of chemical or biologic composition similar to those of cetuximab
- Pregnancy, breastfeeding, or expecting to conceive or father children within the projected duration of the trial, starting with the screening visit through 6 months after the last dose of trial treatment
- Ongoing or active infection, including active tuberculosis or known infection with the human immunodeficiency virus (HIV). Patients with chronic, stable infections such as hepatitis C with an undetectable viral load, or HIV

infection on highly active antiretroviral therapy with undetectable viral load are allowed on the clinical trial.

- Ongoing treatment with other investigational agents.
- Any of the following cardiac conditions:
  - uncontrolled or poorly-controlled arrhythmia or uncontrolled cardiac insufficiency
  - uncontrolled or poorly-controlled hypertension (>180 mmHg systolic or > 130 mmHg diastolic)
- Any of the following conditions:
  - serious or non-healing wound, ulcer, or bone fracture
  - history of abdominal fistula, gastrointestinal perforation, or intra-abdominal abscess within 28 days of study enrollment
  - history of cerebrovascular accident (CVA) or transient ischemic attack within 12 months prior to study enrollment
  - history of myocardial infarction, ventricular arrhythmia, stable/unstable angina, symptomatic congestive heart failure, coronary/peripheral artery bypass graft or stenting or other significant cardiac disease within 6 months prior to study enrollment
  - history of arterial or venous thrombosis/thromboembolic event, including pulmonary embolism within 6 months of study enrollment
  - any condition requiring the use of immunosuppression, excluding rheumatologic conditions treated with stable doses of corticosteroids
  - Use of herbal supplements (St. John's Wort, gingko biloba, etc.) within one week of cetuximab treatment

For patients who do not meet eligibility criteria for Step 2 of the study, the tissue from the research biopsy will be released to the TSB Biobank or back to surgical pathology if needed for a clinical diagnosis.

### **5.3 Strategies for Recruitment and Retention**

The most common method that will be used to recruit subjects is through pre-screening of medical records for patients of a study physician. Members of the study team will preview the schedules of the study physicians to determine the gross eligibility of upcoming patients. When a patient may meet gross eligibility, study team members will notify the physician. At the patient's next clinic visit, the physician may then include a discussion about study participation with the patient.

#### **5.3.1 Subject Remuneration**

Subjects are eligible to receive up to \$200 for participating in this study to offset the barriers of the extra research procedures and visits. Participants will be provided remuneration in the amount of \$100 after the research biopsy, and \$50 after each CTX administration.

## **5.4 Treatment Assignment Procedures**

Not applicable. This is a single arm Window of Opportunity study.

## **5.5 Subject Withdrawal**

Subjects may withdraw voluntarily from the study or the investigator may terminate a subject's participation.

### **5.5.1 Reasons for Withdrawal**

In addition to discontinuation from therapy related to toxicities as outlined in the Halting Rules of Section 9.5, a subject will also be discontinued from protocol therapy and followed up per protocol under the following circumstances:

- Documented disease progression
- The treating physician thinks a change of therapy would be in the best interest of the subject.
- The subject requests to discontinue protocol therapy, whether due to unacceptable toxicity or for other reasons.
  - If a subject decides to prematurely discontinue protocol therapy (“refuses treatment”), the subject should be asked if he or she may still be contacted for further scheduled study assessments. The outcome of that discussion should be documented in both the medical records and in the electronic case report form (eCRF).
- A female subject becomes pregnant.
- The subject meets an exclusion criterion (either newly developed or not previously recognized) that precludes further study participation.

Subjects will be removed from protocol therapy and the site investigator notified when any of the criteria listed above apply. The reason for discontinuation of protocol therapy will be documented on the eCRF.

### **5.5.2 Handling of Subject Withdrawals or Subject Discontinuation of Study Intervention**

If a subject decides to withdraw from the study (and not just from protocol therapy) all efforts should be made to complete and report study assessments as thoroughly as possible. The study team should contact the subject or a responsible relative by telephone to establish as completely as possible the reason for the study withdrawal. A complete final evaluation at the time of the subject's study withdrawal should be made with an explanation of why the

subject is withdrawing from the study. If the reason for removal of a subject from the study is an adverse event, it will be recorded on the eCRF.

If a subject is unevaluable for safety and efficacy endpoints (i.e., lacks molecular/correlative studies, and creation of PDXs, subject has not received both cetuximab doses in their entirety and/or has not had surgical resection of the tumor), then the subject will be replaced at the discretion of the principal investigator.

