## **8.2.3 Specimen Preparation, Handling, and Storage**

### **Research Biopsy**

**Processing of specimen:** The tissue obtained for research biopsy will be placed in culture media or saline, stored at room temperature and provided to the biologic correlate study team within 3 hours post-surgery. The samples will be identified with the research study number and "research biopsy". The label will be stripped of all patient identifiers, such as MR number or dates. If squamous cell carcinoma is NOT confirmed, the tissue from the research biopsy will be relinquished to the TSB Biobank or surgical pathology based on clinical need.

Approximately 1/3 of the research biopsy will be formalin fixed and paraffin embedded. The remaining tissue will be used directly in mice to establish the first panel of PDX from patients with known sensitivity or resistance to cetuximab.

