### **Tumor Tissue**

**Processing of specimen:** The study team will process and embed the fresh tissue obtained from the pathology department to an FFPE block for downstream studies. Alternatively, the biologic correlate study team will request 20 x 5 µm unstained FFPE slides from the diagnostic tissue after surgical pathology clinical review is complete. The specimens will be labeled with the research study number, "surgical resection," and section number, if applicable. The label will be stripped of all patient identifiers, such as the medical record number or dates.

Research Tissue samples and PDXs within the context of this protocol will be maintained under the supervision of [name] located at:  
University of Wisconsin  
[name]

[name]  
[name]

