### 12.2 Sample Size Considerations

We plan to enroll 36 HNSCC patients, powered on the basis of the primary study endpoint: the clinical response rate to cetuximab according to RECIST criteria in low AXL vs. high AXL patients (measured using VECTRA/inForm software). Previous data show that 1 in 3 patients respond to cetuximab, and about one-third (21/57 or 37%) of HNSCC patients have high AXL expression. This sample size is based on 90% power to detect a difference between a response rate of 20% in the high AXL (2+ or 3+) group vs. 65% in the low AXL (0 or 1) group, with an expected ratio of 2:1 low vs. high AXL expression participants. One-sided type I error was fixed at 5%.

For evaluation of safety endpoints, any participant that undergoes a research biopsy will be included. For evaluation of efficacy, molecular/correlative studies, and creation of PDXs, participants must receive both cetuximab doses in their

entirety and have surgical resection of the tumor. If a participant is unevaluable for these endpoints, then the patient will be replaced at the discretion of the principal investigator.

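### Sections 5.5.2 and 12.2 give conflicting evaluability rules: 5.5.2, read literally, lets a failed xenograft make a patient unevaluable, and baseline AXL has no backup tissue source.

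*Combined protocol and SAP*

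**What the plan says.** Section 5.5.2 explains what makes a subject unevaluable for the safety and efficacy endpoints. Its list runs "lacks molecular/correlative studies, and creation of PDXs, subject has not received both cetuximab doses in their entirety", and then adds absence of surgical resection. Such a subject may be replaced at the principal investigator's discretion.

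Section 12.2 reuses much of this wording in a different role. For safety, having had the research biopsy is enough. For the rest it says "For evaluation of efficacy, molecular/correlative studies, and creation of PDXs, participants must receive both cetuximab doses" in full, and must also have the tumour resected. PDX creation is here one of the things evaluated, not a condition. Section 3.2.3 lists PDX establishment as exploratory.

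On tissue, section 8.2.3 (Research Biopsy) says "Approximately 1/3 of the research biopsy will be formalin fixed and paraffin embedded. The remaining tissue will be used directly in mice". The same section assigns the fixed third to total and phosphorylated AXL, EGFR and HER3, and to the baseline side of the Ki67 change. For the surgical specimen, sections 4 and 8.2.3 (Tumor Tissue) offer an alternative source: "unstained FFPE slides from the diagnostic tissue after surgical pathology clinical review is complete". No alternative is named for pre-treatment AXL.

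**The concern.** Whether a tumour grows in mice is a laboratory result. It says nothing about whether the patient was treated, measured and scored for AXL as planned, so it should not decide evaluability for the primary endpoint. Under the literal 5.5.2 wording it can. Section 4 describes an open-label, single-arm trial, section 8.1 has the treating physician measure response, and neither 5.5.2 nor 12.2 says when, or blind to what, replacement is decided. Replacement could therefore be decided after response is known.

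The safety conflict is more direct. A patient who had the biopsy and one dose but no second dose is in the safety set under 12.2 and unevaluable for safety under 5.5.2.

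Separately, a patient whose fixed tissue holds no scorable tumour has no AXL value and cannot enter the primary test in section 12.4, which relates continuous AXL to response.

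**Working it through.** **1. The two rules side by side**

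| Patient | 5.5.2, literal | 12.2 |
|---|---|---|
| Both doses, resected, AXL and response known, no PDX | Unevaluable for safety and efficacy; replaceable | Meets the efficacy conditions; counted for safety |
| Biopsied, missed a dose or surgery | Unevaluable for safety and efficacy | Counted for safety; not for efficacy |
| Both doses, resected, no AXL result | Unevaluable, if lacking AXL counts as lacking the molecular studies | Meets the efficacy conditions, but cannot enter the section 12.4 test |

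The first two rows are contradictions. The third shows that 12.2 does not state all that the primary analysis needs.

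**2. The plan's own sample size**

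Inputs, all from 12.2: "We plan to enroll 36 HNSCC patients, powered on the basis of the primary study endpoint"; "90% power to detect a difference between a response rate of 20% in the high AXL (2+ or 3+) group" against "65% in the low AXL (0 or 1) group"; a 2:1 low-to-high ratio; one-sided 5% error. With the unpooled normal approximation:

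n_high = (1.645 + 1.282)² × [0.20×0.80 + (0.65×0.35)/2] / 0.45² = 8.564 × 0.27375 / 0.2025 = 11.58, rounded up to 12.

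Then n_low = 24 and the total is 36, as stated. Power at 12/24 is Φ(0.45/√(0.16/12 + 0.2275/24) − 1.645) = Φ(2.979 − 1.645) = 90.9%. Other methods do not give 36 (pooled one-sided: 42), so the unpooled form is used below as a yardstick only; the planned test is a Wilcoxon rank sum test. Section 12.2 states no dropout allowance.

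**3. What a literal 5.5.2 could cost**

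The documents give no engraftment rate, so the rates here are assumptions. Evaluable N = 36 × rate (rounded); treated patients needed to keep 36 evaluable = 36 / rate (rounded up); power uses the formula in step 2.

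| Assumed engraftment | Evaluable of 36 (high/low) | Power, no replacement | Treated to keep 36 |
|---|---|---|---|
| 90% | 32 (11/21) | 88% | 40 |
| 80% | 29 (10/19) | 85% | 45 |
| 70% | 25 (8/17) | 79% | 52 |
| 50% | 18 (6/12) | 68% | 72 |
| 30% | 11 (4/7) | 51% | 120 |

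If 12.2 governs, graft failure removes nobody: N stays 36 and power 90.9%.

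**4. Baseline AXL tissue**

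No failure rate is given. If 5% to 15% of fixed thirds held no scorable tumour (assumed), 36×0.05 = 1.8 to 36×0.15 = 5.4 patients, about 2 to 5, would lose the primary predictor. At 34 (11/23) power is Φ(2.879 − 1.645) = 89%; at 31 (10/21) it is Φ(2.747 − 1.645) = 86%. The existing slide alternative cannot fill this gap, because the resected tumour has already been exposed to cetuximab.

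**The case against.** A reader might infer that the xenograft aim overrides the primary aim, and that the primary sample becomes a selected set of tumours that engraft. The documents do not support that.

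- The statistical section sets efficacy evaluability by doses and resection alone, and PDX work is labelled correlative and exploratory. The 5.5.2 list looks like a garbled copy of the 12.2 sentence.
- The word joining correlative studies and PDX creation in 5.5.2 can mean lacking both. A patient with AXL done and a failed graft is then not caught.
- The only stated consequence is discretionary replacement. Neither 5.5.2 nor 12.4 removes a replaced subject's data from the Wilcoxon test.
- Nothing in the documents links engraftment to AXL or to response, so a direction of bias cannot be claimed.
- AXL tissue is not unprotected. A third of the biopsy is reserved for biomarkers, section 5.1 asks for about 10 cc of tumour and at least 2-3 cores, and section 8.2.2 requires a tumour large enough for the correlative endpoints. How to split tissue between fixation and mice is the investigators' choice.

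All of this stands, and it limits the claim. It does not remove the contradiction, which on safety does not depend on how the PDX phrase is read. Nor does saying that 12.2 governs settle everything: its own replacement sentence refers back to a list of endpoints that includes PDX creation, and it requires neither an AXL result nor the two measurements. The collection rules do not ensure scorable tumour in the fixed third.

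**Conclusion.** Section 5.5.2 is wrong as written against section 12.2. The two disagree on who is evaluable for safety and, on the literal reading, on whether a missing PDX makes a patient unevaluable for efficacy. The sample size of 36 reproduces and is not in question.

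The size of the effect is unknown. It is nil if 12.2 governs. The engraftment table is a worst case that assumes a literal 5.5.2, action on every graft failure, and rates the documents do not supply.

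The missing backup source for baseline AXL is a smaller point and a cheap improvement rather than an error: about 2 to 5 patients under assumed failure rates of 5% to 15%.

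**What to change.** **Section 5.5.2.** Delete safety and PDX creation from the definition of unevaluable and align it with 12.2.

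**Section 12.2.** Keep the existing both-doses and resection conditions for efficacy. Add that the primary analysis also needs a pre-treatment AXL result and both tumour measurements, whatever the PDX outcome. State that replaced subjects who meet these conditions stay in the analysis.

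**Section 8.2.3.** When the fixed research tissue has no scorable tumour, allow unstained slides from the pre-treatment diagnostic biopsy block for AXL, where a block is available, and flag those scores in the data. Availability needs checking: section 5.1 describes joint diagnostic and research sampling only for newly suspected cancer, and the documents do not say that a suitable block is on site for known or recurrent disease.

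**Cost.** Protocol wording, and an extension to the diagnostic block of a slide request already used for the surgical specimen. The downside is a few AXL scores from diagnostic rather than research tissue. The split of the biopsy between fixation and mice need not change.
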